8.1. Product, Dose and Mode of Administration Dose

FSD201 is provided as a 600 mg tablet. Participants will be provided with a wallet containing 3 blister cards (sufficient for 15 days of dosing). Subjects should take one (1) tablet twice daily after food approximately 12 hours apart. The subjects will receive a total of 4 wallets over the course of the study, dispensed at Visits 2, 4 and 6.

8.1.1. Investigational Therapy

All randomized subjects will receive the study drug from Day 0 to Day 56 (Visit 2 to Visit 10). Subjects will take one tablet in the morning and one tablet in the evening (i.e., approximately every 12 hours, approximately at the same time every day, and at least 8 hours apart) according to their randomized treatment arm assignment as described below:

Arm A: FSD201 600 mg tablet *b.i.d.* for oral administration after food.

Arm B: One placebo tablet (i.e., matching 600 mg FSD201 tablets) *b.i.d.* for oral administration after food.

The first dose of the study drug will be taken at the site.

8.2. Description of Compound, Packaging, Labeling, Storage

FSD201: Each white-colored oval Oral tablet formulation contains 600 mg of FSD201 drug substance (ultramicrotonized *N*-(2-hydroxyethyl)hexadecanamide). The excipients used in tablet formulation include Microcrystalline Cellulose, Croscarmellose Sodium, Povidone, Magnesium Stearate, Silicon Dioxide and Polysorbate 80 (vegetal origin).

Placebo: Oral tablet formulation containing Microcrystalline cellulose, Dicalcium Phosphate, Croscarmellose Sodium, Magnesium Stearate and Silicon Dioxide. The placebo tablet will be identical in appearance to the study drug.

Primary and Secondary Packaging: Tablets are provided in blister cards of 10 tablets per card, 3 cards per wallet, sufficient for 15 days of dosing.

Labelling: The blister cards will not be labelled individually. The wallet of three blister cards will be labelled according to applicable regulations.

Storage: The blister cards should be stored in the wallet bearing the study label. The investigational product should be stored at room temperature (15-25°C) out of reach of children.

8.2.1. Rescue Medication

Acetaminophen (maximum daily dose 3,000 mg) or diphenhydramine (maximum daily dose 300 mg) is allowed, starting at the screening visit.

8.2.2. Concomitant and Prohibited Medication

Medications taken for pain associated with chronic widespread musculoskeletal nociceptive pains (arising from neurogenic inflammation) secondary or likely “idiopathic MCAS” during the 17 days before the Screening Visit will be recorded in the case report form.

Concomitant use of the following medications or therapies could influence the evaluation of the study drug's efficacy and safety and are prohibited throughout the study:

- Antidepressants (except for selective serotonin reuptake inhibitors)
- Ketamine
- Opioid agonists
- Mast cell stabilizers (e.g., cromolyn sodium, ketotifen, hydroxyurea)
- Mast cell inhibitors (e.g., montelukast, zafirlukast, zileuton, petosan)
- Chemotherapeutic agents (e.g., imatinib, masitinib, dasatinib, nilotinib)
- Intravenous immune globulin (IVIG)
- NSAIDs
- Cannabinoids
- Herbal remedies/supplements containing palmitoylethanolamide

Procedures that may have efficacy in reducing chronic musculoskeletal nociceptive pain are prohibited unless stable for 4 weeks before the Screening Visit, for example, nerve block,

iontophoresis, laser therapy, acupuncture, spinal cord stimulation therapy, transcutaneous electrical nerve stimulation. Stable procedures should be continued for the duration of the study.

The following medications are permitted if they have been at a stable dose (defined as no change to the regimen and the subject reports taking the medication as prescribed) for at least 4 weeks before the Screening Visit, and the dose will remain unchanged during the study:

- Sedatives (e.g., zopiclone, zolpidem, benzodiazepines except lorazepam, temazepam, oxazepam, midazolam);
- Aspirin (low dose, ≤ 325 mg once daily, for cardio prophylaxis)
- Histamine blockers
- Naltrexone (opioid antagonist)
- Gabapentinoids and other anticonvulsants
- Muscle relaxants
- Local anesthetics
- Topical pain mediations

Stable doses of the selective serotonin reuptake inhibitors (SSRIs) are allowed to treat depression if the dose is stable for 60 days before Screening Visit.

8.2.3. Treatment Duration

Each subject will participate in the study for a maximum of 80 days, including a screening period of up to 17 days, a 56 day double-blind treatment period, and a 1-week post-treatment follow-up period.

After their last study drug intake (Day 56), a safety follow-up assessment 7 days (7 ± 2 days) will occur. Follow-up on SAEs and AEs will continue until resolution of the event or until a stable condition is reached. Any SAEs occurring within 7 days after the last IMP (Investigational Medicinal Product) intake will be collected.

9. Materials

The Sponsor will provide at no cost the investigational medicinal product to be used. In addition, the App will be provided at no cost. Patients can choose to have the App installed on their own device, or a device can be provided by the site at no cost.

10. Selection and Withdrawal of Subjects

10.1. Inclusion Criteria

1. The subject is ≥ 18 and ≤ 75 years of age at the time of signing ICF

2. Clinical diagnosis of idiopathic MCAS (in the presence or absence of a generalized hypermobility spectrum disorder (G-HSD) or Ehlers-Danlos Syndrome (EDS)) as per the global consensus diagnostic criteria (consensus-2 criteria (Afrin et al., 2021);
 - a) Medical history shows a constellation of clinical complaints attributable to pathologically increased mast cell (MC) activity (MC mediator release syndrome)
 - b) Medical history of symptomatic response to inhibitors of MC activation or MC mediator production or action
3. Adults with widespread chronic nociplastic pain (in three or more body regions)
4. Chronic pains of intensity ≥ 4.0 but ≤ 9.0 on a Numeric Pain Rating Scale, symptom duration of >6 months
5. Subject signed a Research Ethics Board (REB) or Institutional Review Board (IRB) approved written informed consent and privacy language (Health Insurance Portability and Accountability Act (HIPAA) and Personal Information Protection and Electronic Documents Act (PIPEDA) authorization before performing any study-related procedures
6. The subject is considered reliable and capable of adhering to the protocol (e.g. able to understand and complete forms and questionnaires, visit schedule, or medication intake according to the judgment of the investigator)
7. Subject agrees to use only acetaminophen (up to 1000 mg per dose and not to exceed 3000 mg/day) or diphenhydramine (up to 300 mg/day) as rescue medication for chronic widespread musculoskeletal nociplastic pains throughout the trial
8. The subject is willing to maintain current activity and exercise levels throughout the study
9. During the study, the subject agrees not to initiate or change any non-pharmacologic interventions (including chiropractic care, physical therapy, psychotherapy, and massage therapy). Any ongoing non-pharmacologic intervention must be stable for at least 4 weeks before screening and should be continued for the duration of the study
10. Female subjects of childbearing potential must have a negative serum pregnancy test at the Screening Visit and a negative urine pregnancy test at Randomization Visit
11. Female subjects of childbearing potential must use an acceptable method of birth control. Acceptable birth control includes total abstinence from heterosexual intercourse, a vasectomized partner, intrauterine device, or double barrier method including condoms, sponge, diaphragm, contraceptives (oral, parenteral, or transdermal), or vaginal ring with spermicidal jellies or cream. Subjects considered not of childbearing potential must be surgically sterile (total hysterectomy, bilateral salpingo-oophorectomy, or tubal ligation) or be more than one year post-menopausal, defined as a complete cessation of menstruation for at least one year. Male subjects who are sexually active must use an acceptable method of birth control. Acceptable birth control includes total abstinence from heterosexual intercourse, or use of a double barrier method including condoms sponge, diaphragm, contraceptives (oral, parenteral, or transdermal), or vaginal ring with spermicidal jellies or cream used by partner. Periodic abstinence and withdrawal are not acceptable methods of contraception.
12. The subject is in good health as judged by the investigator, based on medical history, physical examination, serum chemistry, hematology, and urine analysis

13. At the screening visit, the body mass index (BMI) is between 18 and 39 kg/m²
14. The subject is sufficiently fluent in English language to answer the questionnaires in clinic and on the App.

10.2. Randomization Criteria

1. The subject is compliant with daily App entries during the baseline period, as defined by the completion of a minimum of 5 of 7 daily NPRS scores
2. The average daily pain intensity scores on the NPRS are ≥ 4.0 and ≤ 9.0 over the last seven days before the Randomization Visit

10.3. Exclusion Criteria

1. The subject has pain that cannot be clearly differentiated from or that could interfere with the assessment of chronic musculoskeletal nociplastic pain secondary likely to idiopathic MCAS (e.g. post-herpetic neuralgia, traumatic injury, prior surgery, complex regional pain syndrome)
2. Adults with chronic cancer pain
3. Adults with inflammatory connective tissue disorder or rheumatological disorder-related pain, e.g. rheumatoid arthritis
4. Adults with focal musculoskeletal pain
5. Adults with skin diseases (e.g., chronic urticaria, pemphigus, lupus, rosacea etc.)
6. Adults with endocrinological disorders (e.g., acute hypothyroidism, acute adrenal insufficiency etc.)
7. Adults with systemic gastrointestinal conditions (e.g., Inflammatory bowel disease)
8. Significant psychological comorbidities: PHQ-9 score >20 ; and GAD-7 score >15 (indication of severe anxiety that could interfere with accurate logging of pain ratings)
9. Current or recent (within 12 months of screening) history of a substance use disorder including cannabinoid or alcohol use disorder as defined by the Diagnostic and Statistical Manual of Mental Disorders (5th edition; DSM-5)
10. Subject has neurologic disorder unrelated to chronic widespread musculoskeletal nociplastic pains (e.g., phantom limb from amputation, vitamin B12 deficiency, chronic inflammatory demyelinating polyneuropathy), circulatory disorder (e.g., peripheral artery disease), a skin condition in the area of neuropathy that could alter sensation (e.g., plantar ulcer), or other painful conditions (e.g., arthritis) that, in the judgment of the investigator, could interfere with reporting of pain due to chronic widespread musculoskeletal nociplastic pains
11. Current severe or uncontrolled major depressive disorder or anxiety disorders. Mild to moderate major depression or anxiety disorders are permitted provided that the investigator assesses the patient as clinically stable and appropriate for entry into the study. Stable doses of SSRIs are allowed for the treatment of depression if the dose is stable for 60 days before Screening Visit

12. Subject has a history of suicide attempt or suicidal behaviour within the last 12 months or has suicidal ideation within the previous 12 months or who is at significant risk to commit suicide, as judged by the Investigator at Screening or during the treatment period
13. The subject is currently using protocol-specified prohibited medications.
14. Positive urine drug screen for illegal or non-prescribed drugs at the Screening Visit or during the treatment period
15. Pregnant or lactating females or females planning to become pregnant during the study or within 28 days following the last dose of study medication
16. Male patients planning a partner pregnancy or sperm donation during the study or within three months following the last dose of study medication
17. Patients with active malignancy or history of malignancy, except for basal cell or squamous cell carcinoma and actinic keratosis. Basal cell carcinoma and small squamous cell carcinoma of the skin which have been excised according to guidelines within the last 5 years or in situ cervical carcinoma that has been fully treated and shows no evidence of recurrence are allowed
18. Positive human immunodeficiency virus (HIV), hepatitis B or hepatitis C laboratory result
19. Any clinically significant unstable medical abnormality or acute or chronic disease of the cardiovascular, gastrointestinal, respiratory, hepatic, or renal systems. Subject with aspartate transferase or alanine transferase > 2.5 times the upper limit of normal (ULN) or alkaline phosphatase > 3.0 times ULN
20. Any clinically significant deviation from normal in physical examination, vital signs, or clinical laboratory tests, as determined by the investigator
21. Known history of seizure disorder, epilepsy, convulsions, or increased intracranial pressure anytime during the subject's life except for pediatric febrile seizures
22. Subject has received an investigational therapy of any kind within 28 days or 5 half-lives, whichever is longer, before Screening Visit
23. Subject has had known hypersensitivity or intolerance to the use of PEA, diphenhydramine (e.g. Benadryl) or acetaminophen (e.g. Tylenol) and/or their associated formulation components
24. The subject is a member of the site staff or relative of a staff member
25. Individuals with high baseline serum tryptase levels suggestive of Primary or Secondary MCAS (defined as above the normal range of 2.2 to 13.2 µg/L)

10.4. Subject Withdrawal or Replacement

A subject can withdrawal at any time for any reason. Subjects will be withdrawn if they are unable to receive a dose.

10.5. Planned Sample Size

The planned sample size for this study is based on making a Go/No-Go evaluation, focussing on the percentage of patients achieving the reduction in NPRS score, that is, using the binary responder endpoint. A decision criterion is applied with possible decision outcomes being 'Go'

(suggests FSD201 warrants further development), ‘Stop’ (or no-Go, suggests further development of the FSD201 should stop), and ‘Pause’ (inconclusive, additional investigation should be performed before a decision is made). This decision framework was published by [Lalonde et al., \(2007\)](#) and [Frewer et al., \(2016\)](#). Note that these decision criteria will not be definitive as the final decision to continue development will be based on more than just the responder endpoint.

For this decision framework, a lower reference value (LRV) and a target value (TV) are defined for the treatment effect (i.e., difference in the drug response rate between FSD201 and placebo) as follows:

- LRV: The minimum treatment effect below which there is no desire to continue development the compound.
- TV: The targeted treatment effect above which the compound is expected to replace the current standard of care in terms of efficacy

The Go/No-Go calculations are based on the TV of a 30% difference between FSD201 and placebo, and the minimum difference to be considered for further development being 10% (LRV). Furthermore, the calculations have been made such that there is at most 30% probability of a false-go, i.e., there is at least 70% desired confidence that the treatment effect is better than a 10% improvement (LRV), given that a Go decision is made. Similarly, there is a maximum of 10% false-stop risk, i.e., a maximum probability that the treatment effect is better than a 30% improvement (TV), given a Stop decision is made. Finally, it is assumed that the placebo response rate is 20%.

2:1 randomisation

A total sample size of 60 patients (40 on FSD201 and 20 on placebo) has been chosen to balance the needs to minimize the probability of ‘Pause’ whilst maintaining reasonable recruitment cost and time. [Table 4](#) shows the probabilities of making a Go, Pause or Stop decision.

True Treatment Effect	Go	Pause	Stop
TV (30%)	85.2%	4.3%	10.4%
LRV (10%)	25.7%	7.5%	66.8%

Sum of the probabilities may not be 100% due to rounding for display

Table 4 Probabilities of Go, Pause or Stop Given the True Treatment Difference

11. Efficacy

Subjects will report daily average Numerical Pain Rating Scale (NPRS), their Daily Sleep Interference Scale (DSIS), their rescue medication and Investigational Compliance each day using the App.

The questionnaires on efficacy to be performed during the clinic visits include:

Patients Health Questionnaire (PHQ-9), Generalized Anxiety Disorder (GAD-7), Patient Global Impression of Change (PGIC), Anxiety – Short Form 8a (PROMIS), Sleep Disturbance – Short Form 8a (PROMIS), Pain Interference – Short Form 8a (PROMIS), Fatigue – Short Form 8a (PROMIS), General Life Satisfaction – Short Form 5a (PROMIS), Pain Catastrophizing Scale (PCS). Refer to the [Study Procedures and Evaluations](#) to determine which questionnaires are performed at each visit.

12. Safety

The safety and tolerability of FSD201 will be evaluated based on an assessment of treatment-emergent adverse events (TEAEs), clinical laboratory evaluations and physical examinations.

12.1. Biomarkers

Blood samples for analysis of inflammatory cytokines will be collected at Visit 2, Visit 4, Visit 6 and Visit 10. Blood sample collection will be captured in the source and recorded into the Electronic Case Report Form (eCRF).

12.2. Exploratory FSD201 plasma concentration

Blood samples for analysis of FSD201 will be collected on Visit 2, Visit 4, Visit 6 and Visit 10. Blood sample collection and processing times will be captured in the source and recorded into the eCRF, along with time of last test article intake (by patient recall). Blood samples should be processed according to the provided procedure as soon after collection as possible.

12.3. Definitions of Adverse Events

Per International Council for Harmonization (ICH) E2A: An adverse event (AE) is any untoward medical occurrence in a patient or clinical investigation subject administered a pharmaceutical product and which does not necessarily have to have a causal relationship with this treatment. An AE can therefore be any unfavourable and unintended sign (including an abnormal laboratory finding, for example), symptom, or disease temporally associated with the use of a medicinal product, whether or not it is considered to be related to the medicinal product.

Medical interventions such as surgeries, diagnostic procedures, and therapeutic procedures are not AEs, but the action taken to treat the medical condition. They should be recorded as treatment of the AEs.

Use the following categories for assigning the certainty of the relatedness:

- **Not Related:** A causal relationship between the study drug and the AE can be easily ruled out (e.g., based on the temporal sequence, absence of a reasonable pathophysiological mechanism, or direct evidence of actual cause).
- **Unlikely Related:** A clinical event, including a laboratory test abnormality, with a temporal relationship to drug administration which makes a causal relationship improbable, and for which other drugs, chemicals, or underlying disease provide plausible explanations.
- **Possibly Related:** A clinical event, including a laboratory test abnormality, with a reasonable time sequence to administration of the drug, but which could also be explained by concurrent disease or other drugs or chemicals. Information on drug withdrawal may be lacking or unclear.
- **Probably Related:** A clinical event, including a laboratory test abnormality, with a reasonable time sequence to administration of the drug, unlikely to be attributed to concurrent disease or other drugs or chemicals, and which follows a clinically reasonable response on withdrawal. Rechallenge information is not required to fulfill this definition.
- **Definitely Related:** A clinical event, including a laboratory test abnormality, which is a known effect of the drug, follows an obvious sequence of time from the drug's administration, and ceases with discontinuation of the drug. Rechallenge information is not required to fulfill this definition.

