7.1.7. Withdrawal/Discontinuation Procedures

A subject may be discontinued from the study at the discretion of the Investigator for medical reasons, or if the subject wishes to withdraw. **Subjects who do not meet the additional criteria for entering the Treatment Period at Visit 2 will be discontinued from the study and considered screen fails.** Women who become pregnant during the study and males whose partners become pregnant during the study will immediately be discontinued from the study. Refer to [Section 12.8](#) for Pregnancy report criteria. Subjects may, at the Investigator’s discretion, also be discontinued at any time due to non-adherence to treatment regimen (e.g., <80% of the doses taken, failed urine drug test) and missed visits. If a subject does not return for a scheduled visit, every effort will be made to contact the subject, and document the subject outcome, if possible.

Based on previous studies of PEA and the FSD201 Phase 1 trial, the most likely AEs would be related to gastrointestinal intolerance and/or diarrhea. Based on this, laboratory changes consistent with severe diarrhea including a decrease in kidney function ($\text{eGFR} < 60 \text{ mL/min/1.73m}^2$) or hyperkalemia/hypokalemia (serum potassium $< 3.0 \text{ mmol/L}$ or serum potassium $> 5.5 \text{ mmol/L}$) will cause the patient to be discontinued from treatment. In addition, patients who experience a single SAE probably related to the study drug will also be discontinued (whether or not this SAE is related to gastrointestinal intolerance/diarrhea). Individual stopping criteria are summarized in Table 3.

Stopping Criteria	Value for Stopping
Kidney Function (eGFR)	<60 mL/min/1.73m ²
Potassium	<3.0 mmol/L or >5.5mmol/L
Development of an SAE probably related to the study drug	1 SAE

Table 3 Individual Stopping Criteria

All subjects who withdraw or are discontinued by the Investigator (for any reason) will have an Early Termination Visit performed within 14 (\pm 2) days of discontinuation or withdrawal. If subjects have ongoing AEs at the time of discontinuation, the site should follow up with the patient until all AEs are resolved or closed.

The study will be stopped if there are four individuals with SAEs probably related to the study drug in the FSD201 treatment group. This represents 10% of the expected 40 patients in the FSD treatment group.

8. Treatment Plan

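### Probably Related requires a withdrawal response, so a fatal or irreversible SAE may not be counted toward the study stop

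*Combined protocol and SAP*

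**What the plan says.** Section 12.3 sets out five grades of relatedness. For Probably Related, the event must be "unlikely to be attributed to concurrent disease or other drugs or chemicals, and which follows a clinically reasonable response on withdrawal". The sentence that follows relaxes one element only: "Rechallenge information is not required to fulfill this definition". Definitely Related applies to a known effect of the drug that follows an obvious time course "and ceases with discontinuation of the drug". Possibly Related is the only grade that tolerates a gap here: "Information on drug withdrawal may be lacking or unclear". However, it describes events that something other than the drug could also explain.

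The grade is then used three times as a trigger:

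- Section 7.1.7, individual rule: "patients who experience a single SAE probably related to the study drug will also be discontinued".
- Table 3, same rule: "Development of an SAE probably related to the study drug", with one SAE as the stopping value.
- Section 7.1.7, study rule: "The study will be stopped if there are four individuals with SAEs probably related to the study drug in the FSD201 treatment group". The protocol adds: "This represents 10% of the expected 40 patients in the FSD treatment group".

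None of the three says that a higher grade also qualifies. None makes an exception for an event in which a withdrawal response cannot be observed. Section 12.3 is the only place where the term is defined.

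**The concern.** A stopping rule is only as good as the classification that feeds it. Here the qualifying grade includes information that some serious events cannot supply. A death gives no chance to see whether the event improves off drug, and an irreversible injury may show no improvement whatever its cause. If such an event also has no likely alternative explanation, it is the kind of case the study stop exists to count, yet the literal definition does not admit it.

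There is a second, smaller difficulty. For a patient taking every dose, the grade that orders discontinuation depends on what happens after discontinuation.

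At stake is the four-individual rule, the only pre-specified study-level safety stop found in the protocol. Its count should not depend on how each of three sites resolves a gap in a definition.

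**Working it through.** **The plan's own figure.** Inputs: 60 patients randomized 2:1 (section 10.5) and a threshold of four (section 7.1.7). FSD201 arm: 60 × 2/3 = 40. Threshold: 4/40 = 10%. The stated figure reproduces. The question is which events enter the numerator, and that is settled by comparing definitions.

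**The grades in section 12.3 side by side.**

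| Grade | Alternative cause | Withdrawal element | Named in the stopping rules |
|---|---|---|---|
| Not Related | drug link easily ruled out | none | no |
| Unlikely | plausible alternatives exist | none | no |
| Possibly | alternatives could explain the event | may be missing | no |
| Probably | alternatives unlikely | reasonable response on withdrawal | yes |
| Definitely | not mentioned; must be a known drug effect | event ceases on discontinuation | no |

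Two of the five grades contain a withdrawal element, and the rules name one of those two.

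**Four cases run through the table.**

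1. *Reversible SAE, product already stopped.* A withdrawal response can be observed, and section 13.1 has SAEs followed until they resolve, become chronic or stabilize. The event can be graded Probably Related and counted. No problem arises.
2. *SAE in a patient dosing without interruption, no likely alternative cause.* No withdrawal response exists yet, so the literal definition is not met and the individual trigger does not fire. It could be met only after the step it is meant to order. The other two criteria in Table 3, eGFR and potassium, can be read while the patient is dosing and do not share this feature.
3. *Fatal or irreversible SAE, no assessable withdrawal response, no likely alternative cause.* Probably fails on the withdrawal element. Definitely fails because the event does not cease. Possibly fits poorly because it presupposes another possible explanation. Unlikely and Not Related contradict the facts of the case. No grade fits, and the investigator must pick the nearest. If that is Probably, the event counts toward the four; if it is Possibly, it does not.
4. *SAE graded Definitely Related.* It satisfies a stricter definition than the one named. Whether it counts depends on reading the trigger as a minimum grade, which the text does not state.

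Case 3 is the gap that later information cannot close.

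**The case against.** The strongest reply is that sensible investigators will not read the rules this way. The grades are introduced as degrees of certainty, so a definitely related event naturally clears a probably related bar. An event with no likely alternative cause resembles Probably more than Possibly, so many investigators would choose Probably despite the missing withdrawal element. Both points have force. They turn the Definitely Related issue into a clarification, and they are why case 3 *may* go uncounted rather than *will*.

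A reader might infer that the individual rule leaves patients on a drug believed to be harming them. The documents do not support that. Section 7.1.7 lets the investigator discontinue a patient on medical grounds whatever the grade, and section 10.4 requires withdrawal of a patient who cannot take a dose. Harm would need an investigator who thinks the drug probably caused an SAE and continues dosing because of a definitional clause. For a fatal event the individual rule is moot.

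A reader might also infer that SAE reporting is affected. It is not: section 13.1 requires every SAE to be reported irrespective of causality, and section 13.2 sets a lower causality bar for expedited reports.

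What remains is that none of these safeguards determines which events count toward the four. The sponsor's right to terminate at any time (section 16.4.4) is discretionary and does not repair the count.

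**Conclusion.** The point holds as a low-priority correction. Read as written, sections 12.3 and 7.1.7 together leave a fatal or irreversible SAE, with no assessable withdrawal response and no likely alternative cause, without a grade that fits. It may therefore be left out of the study stop. The circularity in the individual trigger is real on the page but largely covered in practice. The silence on Definitely Related is a wording gap that most readers would fill correctly.

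The number of SAEs affected is probably very small. Section 4.3 reports no SAEs in the Phase I programme of 48 healthy subjects. That evidence is limited: those subjects were healthy and repeat dosing lasted seven days, against 56 days in patients here.

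It is tempting to conclude that the working threshold is higher than four, or to compute the chance that the stop is missed. The documents support neither. They give no SAE rate and no basis for assuming what share of events would be ungradable, so no effective threshold or probability is quoted. The conclusion rests on section 12.3 governing the term used in section 7.1.7, where the rules give no cross-reference.

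**What to change.** Two changes:

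- In section 7.1.7 (individual rule and study rule) and in Table 3, write: *SAE at least probably related (probably or definitely) to the study drug*.
- In section 12.3 or 7.1.7, add: *A withdrawal response is required for Probably Related only where product has been stopped and a response can be assessed; it is not required for a patient still on product or for a fatal or irreversible event.*

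The Definitely Related definition can stay as it is, because a case without withdrawal information could then reach Probably Related.

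The edit is short, but it bears on patient safety and study conduct, so under section 16.3.1 it is likely a substantial amendment. It would need regulatory and REB/IRB approval under the IND and CTA before sites use it, followed by brief site retraining. Given the low priority, it could be combined with another amendment. The statistical side effect is a study stop that is slightly easier to reach; the threshold of four individuals is unchanged.
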